### 8.8.3 Data Collection and Follow-up for Withdrawn Participants

If partners no longer wish to receive intervention, then we will retain patients in the intervention. If patients no longer wish to receive the intervention, then partners will no longer receive the intervention either. Regardless of whether partners or patients request not to receive further intervention, we will ask patients and partners to return for outcome assessments. Patients who attend the first group session (i.e., provide a baseline weight) will be considered randomized and will be analyzed according to intent-to-treat principles, regardless of further intervention adherence; these individuals will not be replaced if they drop out subsequent to the first session. Consented participants who do not attend the first session (i.e., do not provide a baseline weight measurement) will not be considered randomized and thus will be replaced.

## 9. Study Procedures

### 9.1 Established Standard of Care:

Current standards of care include consultation by primary care physician or specialist; referral to dietitian; and commercial weight loss programs.

### 9.2 Study Visits

**Table 2. Patient Measurement Schedule**

Baseline medical history, demographics*		Screening Visit – Month 0 – (0-8 weeks)								
Measure		Month								
		0	3	6	9	12	15	18	21	24
Baseline weight	X									
Primary outcome: Weight*	X		X		X		X		X	
Secondary outcomes										
Caloric intake*	X		X		X		X		X	
Physical activity	X		X		X		X		X	
Mediators										
Transformation of motivation*	X	X	X	X	X	X	X	X	X	
Couples' efficacy*	X	X	X	X	X	X	X	X	X	
Outcome efficacy*	X	X	X	X	X	X	X	X	X	
Use of communal coping*	X	X	X	X	X	X	X	X	X	
Social support for diet*	X	X	X	X	X	X	X	X	X	
Social support for physical activity*	X	X	X	X	X	X	X	X	X	
Brief pain inventory-short form *	X		X		X		X		X	
Weight loss methods*			X		X		X		X	
COVID-19*	X	X	X	X	X	X	X	X	X	

\*Assessed from partners as well

### 9.2.1 Screening visit:

The screening visit will occur up to 8 weeks prior to the first group intervention visit. The following measurements will be obtained at screening by the WREN Research Coordinators:

- **Medical history and demographics:** age, race, ethnicity, gender and birth sex, insurance status, financial stress, education, smoking status, alcohol use, illicit drug use, employment status, previous weight loss attempts, history of heart disease, diabetes, cancer, liver disease, and hypertension.
- **Body weight** will be obtained using a calibrated digital scale in light clothing, with shoes removed.
- **Height** will be determined without shoes using a portable or wall-mounted stadiometer.
- **BMI.** The weight and height measures will be used to calculate BMI (weight in kilograms divided by height in meter squared; kg/m^2).
- **Dietary intake** will be assessed using the Automated Self-Administered 24-hour dietary recall (ASA24).(51, 52) Patients will receive training to use the website during the screening visit and may call study staff to ask for assistance. Electronic messages via text and/or e-mail will be sent to notify participants on one randomly determined weekend day and one weekday during the measurement window to complete an unscheduled 24-hour recall. Patients who do not comply within 24 hours will be sent notifications to complete recalls on other dates within the window.
- **Physical activity** will be assessed with FitbitTM watches. Patients will be given their FitbitTM and download the FitbitTM application at their screening visit, along with instructions on how to use and wear it. They will be sent a text and/or e-mail reminder about when to start wearing it continuously for 7 days. Patients will be instructed to return the FitbitTM to the study team if they do not attend the first group session.
- **Transformation of motivation** will be assessed with both Aron's Inclusion of Other in Self (IOS) scale(56) and the Unidimensional Relationship Closeness Scale (URCS).(57) The IOS comprises 7 Venn-like diagrams representing different degrees of overlap between the partner and self. IOS scores range from 1 (completely separate, non-overlapping circles) to 7 (completely overlapping circles). The IOS has produced test-retest correlations >.80 and has been associated with relationship longevity. The theoretical basis supports the transformation of motivation concept in that self-expansion occurs when the interests and experiences of one's partner are integrated into one's self definition. The 12-item URCS has produced highly reliable scores (>.90) across different relationship types, demonstrates measurement invariance across relationship types, and is associated with relational satisfaction.
- **Couple efficacy, outcome efficacy, and use of communal coping measures** have been adapted from previous studies. As with self-efficacy, there is no standardized measure of couple efficacy or outcome efficacy that applies across behaviors; instead, a measurement approach must be tailored to each health behavior. [name] and others have developed items to measure these constructs in the context of smoking cessation,(58) HIV,(59, 60) vasculitis,(61) and colon cancer prevention.(62) We have adapted these items for the current study. Following [name] previous research, we will assess communal coping in three domains (use, confidence, and effectiveness) related to dietary and physical activity changes for both patient and partner. We focus on these three domains because of evidence showing: a) the interdependence of coping behaviors in chronic illness within couples (use)(63); b) the importance of efficacy perceptions in predicting a wide range of health outcomes (confidence); and c) the relevance of behavioral expectations (effectiveness).(64) Use of communal coping for diet and physical activity will be measured with 10 items (e.g., "How often do you and your spouse talk about ways to eat less fat?" 1 never to 5 very often). Confidence in communal coping for diet and physical activity will be measured with 10 items (e.g., "How confident are you that, as a couple, you can talk about ways to eat less fat?" 0 = not at all confident to 10 = extremely confident). Effectiveness of communal coping for diet and physical activity will be measured with 10 items (e.g., "How effective would it be to talk as a couple about ways to eat less fat in getting you to eat less fat?" 0 = not at all effective to 10 = extremely effective). Reliabilities for the all measures have been >.75.
- **Social support for diet and physical activity** will be measured by two additional measures of communal coping, using Ball and Crawford's Social Support and Eating Habits Survey and Social Support for Exercise

Habits Survey, respectively (65). These surveys will be modified to address partners. The measures have produced reliable scores and demonstrated validity in women with overweight/obesity.(66)

- **Brief pain inventory-short form** will ask participants' questions about their pain intensity and its interference in their lives in the last 24 hours.
- **COVID-19** will ask participants' questions about COVID-19 and possible effects of COVID-19 on their own life and their family's lives.

When possible, the partner screening visit will occur at the same time as the patient's screening visit; when impossible, we will allow partners to schedule their screening visit any time before the first patient group session. From the partner, we will obtain medical history/demographics, weight, dietary intake, transformation of motivation, couples' efficacy, outcome efficacy, use of communal coping, social support for diet and physical activity, brief pain inventory-short form, and COVID-19 using the previously described methods.

At the end of the screening visit, once both members of a couple have been deemed eligible, they will be randomized. Patients will be informed of which group date and time they need to attend (which corresponds to their randomization assignment), but they will not be told whether they have been assigned to the partner-assisted vs. patient-only intervention until the first group session. Only patients will attend the first group session, where they will learn of their randomization assignment and be instructed about whether to bring their partner to the next session (depending on arm assignment). Couples will be considered randomized only when their randomization assignment has been disclosed in the first group session. We have done this in previous studies so that patients who do not attend the first group session, where the month 0 "baseline" weight is obtained, do not take a slot in the randomization scheme. To address possible dissatisfaction with randomization in the patient-alone arm, we will emphasize the importance of the patient-only comparator arm during consent and the first group session; emphasize that partners in both arms will be able to participate in assessments; and offer two group sessions to couples in the patient-only arm after final assessments. We have not observed differential dropout in prior studies.

Patients and their partners will return for outcome assessment visits at month 6, 12, 18 and 24 (Table 2). These outcome assessment visits may occur remotely via a video conference if necessary due to public health safety measures. For the patients, at months 6, 12 and 18: weight, dietary intake, physical activity, transformation of motivation, couples' efficacy, outcome efficacy, use of communal coping, social support for diet and physical activity, brief pain inventory-short form and COVID-19 will be measured by using the previously described methods. Additionally, at months 6, 12, 18 and 24, patients will complete a weight loss methods survey to see if there are any other ways they attempted to lose weight other than being in the study. For the transformation of motivation, couples' efficacy, outcome efficacy, use of communal coping, social support for diet and physical activity, brief pain inventory-short form, weight loss methods, and COVID-19 surveys, these will be sent ahead of their visits as a REDCap link via text and/or e-mail. The surveys will be completed at the outcome assessment visit if patients and partners do not complete them ahead of time, on their own. At month 24: weight, surveys (weight loss methods and COVID-19), dietary intake and physical activity assessments will be obtained. For the partners, all of the same measurements will be obtained at the same time-points except for physical activity. All outcome assessment visits will be completed by the WREN Research Coordinators. If patients or partners are unable to attend an in-person outcome assessment visit due to illness or public health safety measures, then we will collect their self-reported weight photos via a DOS REDCap link.

At months 3, 9, 15 and 21, transformation of motivation, couples' efficacy, outcome efficacy, use of communal coping, social support for diet and physical activity, and COVID-19 will be measured for both patients and partners. Patients and partner will be sent the surveys as a REDCap link via text and/or e-mail.

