To enhance recruitment, we will do the following: discuss the study directly with partners to address any questions/concerns; frame weight loss as a couples' issue in recruitment materials; emphasize potential benefits of the intervention and outcome assessments to partners; offer sessions at different times of day; and offer two sessions that address communication to couples in the patient-only arm following the 24-month assessment. If partners no longer wish to receive intervention, then we will retain patients in the intervention (intent-to-treat analyses). If patients no longer wish to receive the intervention, then partners will no longer receive the intervention either. In such cases, we will ask patients (and partners) to return for outcome assessments, as we have done in our previous trials. Other efforts to maximize retention for outcome assessments include: administer the ASA24 online; e-mail/text reminders one week prior to the beginning of each window; place telephone calls and mail letters if participants are non-responsive to electronic reminders; compensate patients and partners \$40 each for completed interim assessments; and increase payments for the final assessment (\$60 each), as we did in the

MAINTAIN trial. In the MAINTAIN trial, 85% of patients returned for final assessments; in the CouPLES trial, 88% of patients and 70% of spouses did.(42, 50)

No participant will be excluded on the basis of race or sex. There have been mixed findings regarding the moderating role of sex in couples-based weight loss interventions. Failure to balance arms with respect to sex could, therefore, affect outcomes. Sex is explicitly accounted for in the study design in that it is a stratification variable. This variable, along with the other stratification variables of patient BMI and partner BMI, will be included in the statistical models for the primary outcome of weight, secondary outcomes of diet and physical activity, and mediation analyses.

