### 8.8.2 When and How to Withdraw Participants

Participants will be educated on the consent form that they are able to withdraw at any time without adverse effects. Participants may withdraw by alerting study staff in person, by telephone, or by email. If participants withdraw from the study, then their status will be updated in the tracking database, and no further contact will be made. Participants may be withdrawn at the discretion of the PI for safety reasons (e.g., self-report of pregnancy) or because they cannot participate meaningfully in the intervention (e.g., cannot communicate well by telephone). These individuals will be informed by study staff in person or by telephone that their participation has ended and the reason for ending their study participation. Their status will then be updated in the tracking database, and no further contact will be made.

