### Patient weight loss initiation intervention (months 1-6, both arms)

Groups of ~11-12 patients will meet every 2 weeks and will be led by an interventionist. Meetings will begin with weigh-ins by research staff (self-report weight photos may be collected via a DOS REDCap link if group classes are delivered remotely and participants will be mailed a scale in this situation) and will involve dietary education, physical activity demonstration, and goal setting. Partners in the partner-assisted arm will attend a subset of these sessions, whereas partners in the patient-only arm will not be permitted to attend group sessions. The group sessions may be delivered via a video call if necessary due to public health measures that would prevent classes from happening in-person. Patients will download the MyFitnessPal application to their mobile phones, to promote

self-monitoring of diet. Although patients will be recruited in Madison, WI, where the PI is located, data from the Fitbit™ will be transmitted to Prompt, a mobile health platform developed by the Duke Digital Health Institute. Using Prompt will save time and money that would be needed to develop a similar resource at UW. Study staff will assist patients during the first group meeting with installing the apps and will be available for ongoing support throughout the trial.

We have reported the theoretical orientation of the initiation and maintenance interventions.(75) The constructs and way they are operationalized are summarized in Table 4. Although the didactic content varies across contacts, the same initiation behavioral strategies are taught and practiced in each group session in months 1-6, and the same maintenance strategies are taught and practiced in each contact in months 7-18. Our model addresses social support during initiation and maintenance.(75) During initiation, patients in a group-based weight loss intervention may receive support from two sources: (1) the intervention setting (interventionist, group members) and (2) their existing social network (friends, family, coworkers). Regarding (1), patients in both arms may derive support from the intervention setting. Regarding (2), in the patient-only arm, patients will not receive instruction on how to solicit social support and partners will not receive intervention. In the partner-assisted arm, couples will receive training in how to engage in communal coping. All the in-person group sessions will be audio recorded.

Table 4

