### 11.2.2.1 Missing Data

Our plans for preventing and dealing with missing data follow the guidelines set forth by the National Research Council's Panel on Handling Missing Data in Clinical Trials. First, we will employ numerous strategies to achieve < 20% patient attrition. Second, as recommended by the panel, we will conduct two general types of sensitivity analyses for our primary analysis. Because we are using full likelihood methods, the primary analysis model above (as well as the exploratory aim analysis model discussed below) is valid under the MAR (missing at random) framework, where missing values may depend on treatment arm, any observed weight measurement, patient sex, and patient and partner *month0* weight. If missing values are related to other measured factors, such as physical activity measurements, then multiple imputation provides a framework for incorporating information from these auxiliary variables while still preserving a parsimonious main treatment effect model.(86) As a first sensitivity analysis, a general, multivariate imputation model will be constructed using all observed weights, treatment arm, and any covariates predictive of missingness. The primary model, specified above, will then be fit to the multiply imputed data, and the estimates and standard errors will be combined using appropriate combining rules. We acknowledge the possibility that data may be MNAR and propose as a second sensitivity analysis to explore MNAR methods, including pattern-mixture models and the toolkit of methods presented in O'Kelly & Ratitch.(87)

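### Remote outcome weights are limited to illness or public health measures; no remote fallback for the month-24 primary weight is written for patients who do not come in for other reasons

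*Combined protocol and SAP*

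**What the plan says.** The primary outcome is patient weight at 24 months (7.1.1), and the analysis is by intent to treat (10.3).

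- **Remote video visits** (9.2.1, outcome assessment paragraph): "These outcome assessment visits may occur remotely via a video conference if necessary due to public health safety measures". No other reason is given.
- **Weight photos at outcome visits** (same paragraph): collected when participants are "unable to attend an in-person outcome assessment visit due to illness or public health safety measures, then we will collect their self-reported weight photos".
- **Existing remote weighing** (9.2.2, weight loss initiation): "self-report weight photos may be collected via a DOS REDCap link if group classes are delivered remotely and participants will be mailed a scale". This is tied to remotely delivered classes.
- **Patients who stop the intervention** (8.8.3): "Regardless of whether partners or patients request not to receive further intervention, we will ask patients and partners to return for outcome assessments". Section 8.5.1 repeats the request for patients who no longer want the intervention: "In such cases, we will ask patients (and partners) to return for outcome assessments, as we have done in our previous trials".
- **Patients who withdraw from the study** (8.8.2): "If participants withdraw from the study, then their status will be updated in the tracking database, and no further contact will be made".
- **Retention measures** (8.5.1, 8.7.5): electronic reminders, calls, letters, online dietary recall, and a $60 payment at month 24. Remote weighing is not listed, and travel costs are not paid.
- **Missing data** (11.2.2.1): "we will employ numerous strategies to achieve < 20% patient attrition".
- **Outcome definition for the model** (10.2, Aim 1): weight measured at in-person study visits.

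**The concern.** The plan wants outcome weights from patients regardless of adherence, but offers a remote route only for two kinds of absence. A patient who has moved unexpectedly, has lost transport, or has stopped the intervention and declines to travel meets neither condition. If that patient does not come in, the month-24 weight is missing under the plan as written, even though staff already have a means of collecting it.

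The stake is avoidable loss of the primary endpoint. Section 11.2.2.1 itself accepts that missing weights may be missing not at random. For such patients an observed weight, even a noisier one, is better than one supplied by a model. The sample size also has little reserve beyond its 20% attrition allowance.

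**Working it through.** **1. Which absences have a remote route?**

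| Situation at an outcome visit | In-person route | Written remote route |
|---|---|---|
| Public health measures | may not be possible | video or photo (9.2.1) |
| Illness | may not be possible | photo (9.2.1) |
| Stopped the intervention, still in the study | asked to return (8.5.1, 8.8.3) | none |
| Unplanned move, or cannot or will not travel | visit stays open | none |
| Withdrew from the study | no further contact (8.8.2) | none, and none should be added |

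The gap is rows three and four.

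**2. Reproducing the plan's sample size (10.1).** Inputs: difference 2.5 kg, SD 19.9 kg, correlation 0.96, power 80%, alpha 5% (two-sided reproduces), m = 15, ICC = 0.01, attrition 20%.

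- t-test of post scores: 2 × [19.9 × (1.960 + 0.842) / 2.5]² ≈ 995 per arm.
- Times 2(1 − 0.96) = 0.08: 79.6, so 80 per arm or 160 in total (162 with the extra participant per arm).
- Design effect 1 + 14 × 0.01 = 1.14: 160 × 1.14 = 182.4 (stated 180).
- Attrition: 180 / 0.80 = 225, or 182.4 / 0.80 = 228 (stated 230).

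Each step is within about 3% of the stated figure.

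**3. Power by number of month-24 weights.** SD of change = 19.9 × √0.08 = 5.63 kg. SE = 5.63 × √(2 / n*), where n* is the evaluable number per arm divided by 1.14. Power = Φ(2.5 / SE − 1.96).

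At the planned loss, 20% of 230 = 46 are missing and 184 are evaluable (92 per arm). Then n* = 80.7, SE = 0.886 kg, and power = Φ(2.82 − 1.96) = 80.5%.

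| Share of the 46 recovered (assumed) | Weights regained | Evaluable | Missing | Power |
|---|---|---|---|---|
| 0% | 0 | 184 | 20% | 80.5% |
| 25% | 11.5 | 195.5 | 15% | 82.9% |
| 50% | 23 | 207 | 10% | 84.9% |
| 100% (ceiling) | 46 | 230 | 0% | 88.4% |

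If loss exceeded the allowance, power would be 78.0% at 25% missing and 75.2% at 30%.

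These figures treat the test as a complete-case comparison of change. The planned mixed model also uses weights from months 6, 12 and 18, so the true effect of missing month-24 weights may be somewhat smaller.

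**4. Price in random error.** The variance of change is 5.63² = 31.7 kg². A home-scale error SD of 1–2 kg (assumption) adds 1–4 kg², or 3–13%, for photo patients only. With 23 photo weights among 207, the average variance rises by at most 23/207 × 13% ≈ 1.4%.

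**The case against.** The strongest case against the point has four parts.

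- **Patients who stop the intervention are not abandoned.** They are asked to return, with reminders, calls, letters, a $60 final payment and two weeks either side of the target date (8.5.1, 8.7.5, 9.2.5). This stands. A reader might infer that they have no way to give the month-24 weight; 8.5.1 and 8.8.3 rule that out. What they lack is a remote fallback.
- **Entry criteria narrow the group.** Planned relocation is an exclusion (8.3), and reliable transport and agreement to attend visits are required (8.2). This also stands. The gap concerns unplanned moves and later changes in circumstances or willingness.
- **The likely gain is limited.** The 20% allowance is described as conservative (10.1). Section 8.5.1 reports 85% return at final assessment in MAINTAIN, although 5.3 gives 80% retention. Patients who withdraw from the study, including those whose participation ends on pregnancy (12.4.4, 12.5.1), are out of reach. Likelihood analysis, multiple imputation and MNAR sensitivity analyses are already planned. This limits the size without closing the gap.
- **In-person weighing protects the endpoint.** Outcome assessors are blinded and participants are not (12.7), and 9.2.1 specifies a calibrated scale, light clothing and no shoes. A photo gives up both protections, and its error could be systematic as well as random. This is a good reason to keep photos as a last resort and to flag them. It is a weak reason to accept a photo from an ill patient but not from one who has moved.

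**Conclusion.** The point holds as a gap in the retention plan. Remote outcome weights are confined to illness or public health measures, and no remote fallback is written for patients still in the study who stop the intervention, move unexpectedly, or cannot or will not travel. No figure in the plan is wrong as a result.

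If 25–50% of the 46 planned losses were recovered, 12–23 weights would be regained and power would rise from about 80.5% to about 83–85%. That is an upper range: the recovery share is assumed, the 46 include study withdrawals who may not be contacted, and the calculation ignores the information the mixed model takes from earlier visits.

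Two stronger readings are tempting but lack support. A reader might infer that these absences are the main way patients leave such a trial and that they go with weight regain; the documents give neither reasons for dropout nor a link to regain. A reader might also infer a bias between arms from unequal loss; 9.2.1 says the team has not seen differential dropout in its earlier studies. The case rests on recovering primary data cheaply.

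**What to change.** A cheap improvement, in four parts:

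1. **Widen the trigger in 9.2.1, and match it in 8.5.1 and 8.8.3.** Suggested sense: if a patient or partner who has not withdrawn from the study does not attend an outcome visit in person, for any reason, then once in-person contact attempts have failed, a video visit or weight photo is obtained within the visit window, with a scale mailed if needed. In-person measurement stays the default. The no-contact rule in 8.8.2 is unchanged.
2. **Align the outcome definition in 10.2, Aim 1.** It refers only to in-person visits, which already sits awkwardly with the photo weights allowed in 9.2.1. State that video and photo weights enter the primary model.
3. **Record the measurement mode and the reason** for each weight not taken in person.
4. **Add a sensitivity analysis** that excludes photo weights.

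The cost is protocol wording, one or two data fields, one extra analysis and some mailed scales; no new system is needed. The downside is noisier weights, not taken by the blinded assessor, for these patients. Some participants might also come to prefer the remote option, which the last-resort condition limits.

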## **12.7 Unblinding Procedure**

Blinding of participants is not possible in behavioral interventions. Only WREN outcome assessors will be blinded.

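### When an in-person outcome visit is not possible, weight is a self-sent photo that nobody is required to observe, although video visits with the blinded coordinators are already allowed

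*Combined protocol and SAP*

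**What the plan says.** Section 9.2.1 sets the clinic standard: body weight "will be obtained using a calibrated digital scale in light clothing, with shoes removed". The same section carries this to months 6, 12 and 18, where weight and the other measures "will be measured by using the previously described methods"; Section 9.2.5 does the same for month 24.

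On who takes the measurement, Section 9.2.1 states: "All outcome assessment visits will be completed by the WREN Research Coordinators". Section 12.7 states: "Blinding of participants is not possible in behavioral interventions", and "Only WREN outcome assessors will be blinded".

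Section 9.2.1 makes two provisions for remote follow-up:

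- Video: "These outcome assessment visits may occur remotely via a video conference if necessary due to public health safety measures".
- Photo: "then we will collect their self-reported weight photos via a DOS REDCap link". The trigger for this route is a patient or partner who is "unable to attend an in-person outcome assessment visit due to illness or public health safety measures".

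Section 9.2.2 says that participants are mailed a scale when group classes are remote, and that weigh-ins at those classes may then be photos. It gives no calibration requirement or weighing conditions for that scale. Section 10.2 (Aim 1) defines the outcome as weight at in-person visits and does not mention photo weights.

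**The concern.** Participants cannot be blinded, so the protection of the primary endpoint rests on a blinded assessor taking the weight under fixed conditions. The photo route moves the measurement to the patient, who knows the arm. The protocol does not say when the photo is taken, what it must show, what the patient wears, or who reads it and whether that person is blinded. A patient weighing alone could pick a favourable time of day, wear less, or send the lowest of several readings. The partner-assisted arm trains couples together in support and joint planning and the other arm does not, so equal weighing habits in the two arms cannot be taken for granted.

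The people and equipment for something better are largely in place. Public-health remote visits may be held by video, coordinators complete all outcome visits, and scales are mailed for remote classes. Ability to join a video call with a camera is an eligibility criterion, listed for patients in Section 2 and for partners in Section 8.2. The text does not bring these together for the one measurement that matters most.

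**Working it through.** **1. The plan's own figure.** Inputs from Section 10.1: difference 2.5 kg, SD 19.9 kg, month 0 to month 24 correlation 0.96, power 80%, type I error 5% (taken as two-sided), ICC 0.01 with groups of 15, attrition 20%.

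- A t-test of post scores needs 995 per arm. Multiplied by 2(1 − 0.96) = 0.08 this is 79.6, so 80 per arm and 160 in total, as stated (162 with the extra participant per arm that the plan mentions).
- Design effect 1 + 14 × 0.01 = 1.14; 160 × 1.14 = 182.4 (plan: 180).
- 180 / 0.8 = 225 and 182.4 / 0.8 = 228 (plan: 230).

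The sample size reproduces to within rounding.

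**2. Precision of the month-24 contrast.**

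- SD of change = 19.9 × √0.08 = 5.63 kg.
- Completers = 230 × 0.8 = 184, or 92 per arm; 92 / 1.14 = 80.7 effective per arm.
- SE = 5.63 × √(2 / 80.7) = 0.886 kg. Power for 2.5 kg is 80.6%.

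**3. Bias if photo weights are used.**

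Bias = (share of month-24 weights sent by photo) × (between-arm difference in the mean self-selection shift).

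Neither term is in the documents. I assume a share of 25% to 75% and a between-arm difference of 0 to 1.0 kg.

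| Share | Difference between arms | Bias | Share of 2.5 kg |
|---|---|---|---|
| any | 0 kg | 0 kg | 0% |
| 25% | 0.3 kg | 0.075 kg | 3% |
| 75% | 1.0 kg | 0.75 kg | 30% |

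At the top of that range, 0.75 / 0.886 = 0.846 standard errors. With no true effect, two-sided type I error is 1 − Φ(1.96 − 0.846) + Φ(−1.96 − 0.846) = 13.5% instead of 5%. With a true effect of 2.5 kg, power is 50.6% if the bias works against the partner-assisted arm (apparent effect 1.75 kg) and 95.6% if it favours that arm (3.25 kg).

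**4. If the shift is the same in both arms.** With equal shares of photo weights, the contrast is unbiased, although weight loss within each arm may be misstated. The remaining cost is noise. If every month-24 weight carried extra error, an added SD of 1 kg gives √(5.63² + 1²) = 5.72 kg and power 79.3%; an added SD of 2 kg gives 5.97 kg and power 75.8%.

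These figures use the simple change from month 0 to month 24 on which the plan was sized. The Aim 1 model tests a linear arm-by-time slope over five visits, so photo weights at months 6, 12 and 18 would also count.

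**5. What an observed weigh-in would and would not restore.** It would restore an assessor-read value and control of clothing, shoes and the moment of weighing. It would not restore the calibrated clinic scale. It would also leave month 0 as it is: that weight is taken by research staff at the first group session and, under Section 9.2.2, may itself be a photo if the session is remote.

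**The case against.** The strongest reply is that this is a pandemic contingency with some detail left out. Several parts of it stand.

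- A reader might infer that the trial's only blinding is lost. The documents do not support that. A photo of a scale display does not reveal the arm to an assessor, and patients were never blinded. What is missing is observation of the weighing.
- A reader might infer that the primary weight at remote visits is a photo. Section 10.2 limits the outcome to in-person visits. On that wording photo weights may not enter the model, and their bias in the primary contrast would then be zero. Sections 9.2.1 and 10.2 have to be reconciled.
- A reader might infer that a blinded coordinator is always on a call. Video is stated for public health reasons only; the photo route also covers illness, where no call is stated.
- The text does not say that the photo is taken outside the call or without instructions. Section 13.2 refers to a manual of procedures, which might hold them.
- The patient intervention is the same in both arms, and both are taught to fix a day and time for self-weighing. Similar habits in the two arms are plausible, so zero belongs in the range.

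The last step, that only a minor clarification is needed, does not follow. The procedure stated in the protocol is a self-reported photo, and a better one is open to the trial with staff and calls it already provides for. Silence on whether the photo is watched is not a safeguard for the primary endpoint.

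**Conclusion.** The point holds as an unprotected measurement, not as broken blinding. When an in-person visit is impossible, the protocol accepts an unobserved, patient-supplied weight with no stated conditions, although for public-health remote visits a blinded coordinator may already be on video. Bias in the arm difference needs two things together: photo weights in the primary model, and weighing behaviour that differs by arm. Neither is established. The size cannot be derived from the documents; 0 to 0.75 kg (0% to 30% of 2.5 kg) is illustrative and rests on the assumed shares and shifts. Error that is equal in both arms costs little. No change to the sample size follows. This is a cheap improvement worth making.

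**What to change.** In Section 9.2.1, state that at a video outcome visit the blinded WREN coordinator watches the weigh-in live and records the reading: light clothing, no shoes, study-mailed scale zeroed on a hard floor, display shown on camera. Say explicitly that a study scale is provided for remote outcome visits, since Section 9.2.2 mentions mailing only for remote classes. Keep the self-sent photo as fallback when there is no call, including illness, or when video fails.

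Record the mode of every weight, month 0 included: in person, observed on video, or photo. Reconcile Section 9.2.1 with Section 10.2 on whether remote weights enter the primary model, and add a sensitivity analysis by mode. Where visits are already complete, recording the mode and who read each photo is still feasible.

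The cost is one paragraph in the protocol or manual, a few minutes on a call already provided for, help with the camera for some patients, and some loss of privacy in being weighed on video. It is small, but not nil.
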